11.4.3 Analyses of safety data

See also [Section 9.2](#).

The summary of safety results will be presented by treatment group. No formal inferential testing will be performed. Summaries will be descriptive in nature.

All safety analyses will be performed on the Safety population using the following common rule:

- The baseline value is defined generally as the last available value before the first double-blind IMP injection. For analyses of changes from baseline for laboratory and vital signs parameters, baseline of the last available value before double-blind or open-label IMP injection may be considered.

Safety analyses will be conducted using data of the DBTP. Besides, safety analyses using data of the DBTP and the OLTP (from the first double-blind IMP injection for alirocumab 150 mg Q4W group and alirocumab 150 mg Q2W group, and from the first open-label IMP injection for placebo group) will be conducted to evaluate long-term safety.

The following definitions will be applied to laboratory parameters and vital signs:

- The potentially clinically significant abnormality (PCSA) values are defined as abnormal values considered medically important by the Sponsor according to predefined criteria/thresholds based on literature review and defined by the Sponsor for clinical laboratory tests and vital signs.
- The PCSA criteria will determine which patients had at least 1 PCSA during the TEAE period, taking into account all evaluations performed during the TEAE period, including unscheduled or repeated evaluations. The number of all such patients will be the numerator for the PCSA percentage.

Adverse events (AE) definition:

- **Pre-treatment AEs** are AEs that develop, worsen, or become serious during the PRE-TREATMENT period.
- **Treatment-emergent AEs (TEAEs)** are AEs that develop, worsen, or become serious during TEAE period.
- **Post-treatment AEs** are AEs that develop, worsen, or become serious during the POST-TREATMENT period.

Drug-induced liver injury:

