- The open-label RESIDUAL TREATMENT period: defined as the time from the day of last dose of open-label IMP injection +22 days up to the day of last dose of open-label IMP injection +70 days (10 weeks).
- The open-label POST-TREATMENT period: defined as the time starting the day after the end of the open-label TEAE period (i.e., 71 days after the day of last dose of open-label IMP injection).

Observation periods below will be analyzed at the first step analysis only.

- The alirocumab exposed TEAE period is defined as follows :
 - For alirocumab 150 mg Q4W group and alirocumab 150 mg Q2W group: The time from the first dose of double-blind IMP injection to the last dose of IMP injection (double-blind or open-label) + 70 days (10 weeks).

- For placebo Q2W group: The time from the first dose of open-label IMP injection to the last dose of open-label IMP injection + 70 days (10 weeks).

The alirocumab exposed TEAE period will include:

- The alirocumab exposed TREATMENT period: defined below:
 - For alirocumab 150 mg Q4W group and alirocumab 150 mg Q2W group: The time from the first dose of double-blind IMP injection to the last dose of IMP injection (double-blind or open-label) + 21 days.
 - For placebo Q2W group: The time from the first dose of open-label IMP injection to the last dose of open-label IMP injection + 21 days.
- The alirocumab exposed RESIDUAL TREATMENT period: defined below:
 - For alirocumab 150 mg Q4W group and alirocumab 150 mg Q2W group: The time from the day of last dose of IMP injection(double-blind or open-label) +22 days up to the day of last dose of IMP injection(double-blind or open-label) +70 days (10 weeks).
 - For placebo Q2W group: The time from the day of last dose of open-label IMP injection +22 days up to the day of last dose of open-label IMP injection +70 days (10 weeks).

The double-blind on-study observation period is defined as the time from the day of first dose of double-blind IMP injection until the last protocol planned double-blind visit of the patient. The last protocol planned double-blind visit is defined as the follow-up visit if done, or a maximum of 20 weeks after the randomization of the patient, for patients not proceeding into OLTP. For patients proceeding into OLTP, the last protocol planned double-blind visit is defined as the end of double-blind treatment period visit (Week 12).

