2.4.3.1 Extent of investigational medicinal product exposure

Injection (alirocumab or placebo)

Double-blind IMP injections are those administered from randomization to completion or discontinuation of the double-blind study treatment. These injections contain:

- placebo Q2W for patients randomized in the Placebo Q2W group,
- placebo Q4W (to maintain the blind) or 150 mg Q4W of alirocumab for patients randomized in the Alirocumab 150 mg Q4W group.

- 150 mg Q2W of alirocumab for patients randomized in the Alirocumab 150 mg Q2W group.

The total exposure during the DBTP will be assessed using descriptive statistics for:

- Duration of double-blind IMP injection exposure in weeks defined as: (date of last dose of double-blind IMP injection +14 – date of first dose of double-blind IMP injection) / 7, regardless of intermittent discontinuations (see [Section 2.5.3](#) for calculation in case of missing or incomplete data). Non-integer values will be rounded to 1 decimal place;
- The total number of double-blind IMP injections by patient.

Duration of double-blind IMP injection exposure will be summarized using number, mean, SD, median, minimum and maximum. In addition, it will be summarized according to the following categories: ≥ 1 day and < 4 weeks, ≥ 4 weeks and < 8 weeks, ≥ 8 weeks and < 10 weeks, ≥ 10 weeks.

The total exposure during the OLTP will be assessed using descriptive statistics for:

- Duration of open-label IMP injection exposure in weeks defined as: (date of last dose of open-label IMP injection +14 – date of first dose of open-label IMP injection) / 7, regardless of intermittent discontinuations (see [Section 2.5.3](#) for calculation in case of missing or incomplete data). Non-integer values will be rounded to one decimal place;
- The total number of open-label IMP injections by patient.

Duration of open-label IMP injection exposure will be summarized using number, mean, SD, median, minimum and maximum. In addition, it will be summarized according to the following categories: ≥ 1 day and < 12 weeks, ≥ 12 weeks and < 24 weeks, ≥ 24 weeks and < 36 weeks, ≥ 36 weeks and < 48 weeks, ≥ 48 weeks.

The total exposure during alirocumab exposed period (defined in [Section 2.4.5](#)) for first step analysis only will be assessed using descriptive statistics for:

- Duration of alirocumab IMP injection exposure in weeks defined as:

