 - For Alirocumab 150 mg Q4W group and Alirocumab 150 mg Q2W group: (date of last dose of IMP injection (double-blind or open-label) +14 – date of first dose of double-blind IMP injection) / 7, regardless of intermittent discontinuations (see [Section 2.5.3](#) for calculation in case of missing or incomplete data). Non-integer values will be rounded to one decimal place;
 - For Placebo Q2W group: (date of last dose of open-label IMP injection +14 – date of first dose of open-label IMP injection) / 7, regardless of intermittent discontinuations (see [Section 2.5.3](#) for calculation in case of missing or incomplete data). Non-integer values will be rounded to one decimal place;
- The total number of alirocumab IMP injections by patient.

Duration of alirocumab IMP injection exposure will be summarized using number, mean, SD, median, minimum and maximum. In addition, it will be summarized according to the following

categories: ≥ 1 day and <12 weeks, ≥ 12 weeks and <24 weeks, ≥ 24 weeks and <36 weeks, ≥ 36 weeks and <48 weeks, ≥ 48 weeks and <60 weeks, ≥ 60 weeks.

Titration

For the OLTP, the number and percentage of patients with an up-titration at Week 24 will be described. Patients with an up-titration are defined as up-titrated patients according to IRT Week 24 transaction with at least 1 injection of alirocumab 150 mg Q2W afterwards.

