2.4.5 Analyses of safety data

Safety analyses will be conducted using data of the DBTP and OLTP. The summary of safety results will be presented separately for the DBTP on the safety population and OLTP on the OLT population. Besides, safety analyses performed on the alirocumab exposed period (see [Section 2.1.4](#)) will be conducted on the alirocumab safety population to evaluate long-term safety at the first step analysis.

The analyses performed on the DBTP will be presented by treatment group while the analyses performed on the OLTP or the alirocumab exposed period will be presented by overall patients. No formal inferential testing will be performed. Summaries will be descriptive in nature. All summaries of safety results described below will be presented for each observation period respectively, unless otherwise noted.

General common rules

All safety analyses will be performed using the following common rules:

- Safety data in patients who do not belong to the safety population (eg, exposed but not randomized) will be listed separately
- The baseline value for both double-blind and open-label treatment period is defined as the last available value before the first double-blind IMP injection, except otherwise specified.
- The potentially clinically significant abnormality (PCSA) values are defined as abnormal values considered medically important by the Sponsor according to predefined criteria/thresholds based on literature review and defined by the Sponsor for clinical laboratory tests, vital signs, and ECG (PCSA defined in the document “Analysis and reporting safety data from clinical trials through the Clinical Study Report (CSR) (Version Number: 3.0)” [[Appendix A](#)])

Considering that the threshold defined in the PCSA list for monocytes and basophils can be below the ULN, the following PCSA criterion will be used for the PCSA analysis of monocytes and basophils:

- PCSA criterion for monocytes: >0.7 Giga/L or $>$ ULN (if $ULN \geq 0.7$ Giga/L);

- PCSA criterion for basophils: >0.1 Giga/L or $>$ ULN (if $ULN \geq 0.1$ Giga/L).
- PCSA criteria will determine which patients had at least 1 PCSA during the TEAE period, taking into account all evaluations performed during the TEAE period, including unscheduled or repeated evaluations.
- The treatment-emergent PCSA denominator by group for a given parameter will be based on the number of patients assessed for that given parameter at least once during the TEAE period.

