2.4.5.1 Analyses of adverse events

Generalities

The primary focus of AE reporting will be on TEAEs, presented in each observation period. Pre-treatment and post-treatment AEs will be described separately.

If an AE date/time of onset (occurrence, worsening, or becoming serious) is incomplete, an imputation algorithm will be used to classify the AE as pre-treatment, treatment-emergent, or post-treatment. The algorithm for imputing date/time of onset will be conservative and will classify an AE as treatment-emergent unless there is definitive information to determine it is pre-treatment or post-treatment. Details on classification of AEs with missing or partial onset dates are provided in [Section 2.5.3](#).

AE incidence tables will present, the number (n) and percentage (%) of patients experiencing an AE by SOC, HLGT (when applicable), HLT (when applicable), and PT. Multiple occurrences of the same event in the same patient will be counted only once in the tables within a treatment phase. The denominator for computation of percentages is the safety population within each treatment group.

Sorting within tables ensures the same presentation for the set of all AEs within the observation period (pre-treatment, TEAE, and post-treatment). For that purpose, the table of all TEAEs presented by SOC and PT sorted by the internationally agreed SOC order and decreasing frequency of PTs within SOCs (in the alirocumab 150mg Q4W group) will define the presentation order for all other tables by SOC and PT, unless otherwise specified. The tables of AEs by SOC, HLT, HLT and PT will be sorted by the SOC internationally agreed order and the other levels (HLT, HLT, PT) will be presented in alphabetical order, unless otherwise specified

Analysis of all treatment-emergent adverse events

The following TEAEs summaries will be generated.

- Overview of TEAEs, summarizing number (%) of patients with any
 - TEAE;
 - Serious TEAE;
 - TEAE leading to death;
 - TEAE leading to permanent treatment discontinuation.
- All TEAEs by primary SOC, HLT, HLT, and PT;
- Number (%) of patients experiencing common TEAE(s) presented by primary SOC, HLT and PT (HLT incidence $\geq 2\%$ in any treatment group), sorted by SOC internationally agreed order and by alphabetic order for the other levels (HLT and PT);

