3 TWO-STEP ANALYSIS

The analysis will be conducted in 2 steps, although no formal interim analysis for efficacy is planned in this study. No multiplicity adjustment for multiple analyses is needed as explained in Section 2.4.4.3.

- First step: Efficacy and safety analyses using data up to 24 weeks after randomization (including 12 weeks double-blind).
 - This analysis will be conducted as soon as all patients have been randomized and have at least all their data up to Week 24 (including 12 weeks DBTP and 12 weeks OLTP) collected and validated.
 - The final analysis of the primary and secondary efficacy endpoints will be performed up to Week 12 time point. The results of this analysis will not be used to change the conduct of the ongoing study in any aspect.
 - [REDACTED]
 - The safety analyses will be performed on all safety data up to the patient's cut-off date defined as the date of Week 24 visit or the date corresponding to 169 days (i.e. 6 months) after first double-blind IMP injection for patients with no Week 24 visit.
- Second step: Long-term safety and efficacy exploratory analysis
 - This analysis will be conducted at the end of the study with all data including the data of the OLTP, and will consist in the final analysis of the safety endpoints and exploratory efficacy assessment during the OLTP.

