4 DATABASE LOCK

Two database locks will be done:

- First database lock (for first analysis): will include all available data on all randomized patients up to date of Week 24 visit for each patient as defined in [Section 3](#).
[REDACTED]
- Final database lock (for second analysis): will include all data, including follow-up, for all randomized patients.
[REDACTED]

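### The combined from-first-alirocumab-dose safety and exposure tables are planned only at the Week 24 cut, so half their exposure categories cannot be filled and study end has no cumulative safety table

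*SAP*

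**What the plan says.** SAP 2.1.4 defines the alirocumab exposed periods. They run from the first double-blind injection for the two alirocumab arms and from the first open-label injection for the placebo arm. The definitions follow the sentence "Observation periods below will be analyzed at the first step analysis only". SAP 2.4.5 says the combined analyses "will be conducted on the alirocumab safety population to evaluate long-term safety at the first step analysis". The restriction recurs for exposure and compliance (2.4.3), hepatitis C and laboratory data (2.4.5.3), vital signs (2.4.5.4) and HbA1c (2.4.6).

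The first step is a Week 24 cut. SAP 3 gives a "cut-off date defined as the date of Week 24 visit", or 169 days after the first double-blind injection if that visit is missing. The first lock (SAP 4) "will include all available data on all randomized patients up to date of Week 24 visit for each patient".

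SAP 2.4.3.1 says total exposure over the combined period "for first step analysis only will be assessed using descriptive statistics for" duration and number of injections. The upper half of the duration categories is "≥ 36 weeks and <48 weeks, ≥ 48 weeks and <60 weeks, ≥ 60 weeks".

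Protocol 11.4.3 plans "safety analyses using data of the DBTP and the OLTP", counted from first alirocumab dose, to evaluate long-term safety. It attaches no step to them. Protocol 11.5.2 makes the second step the final safety analysis on all data. SAP 1.5 and 1.6 both report no modifications.

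**The concern.** The SAP confines the analysis meant to describe long-term safety to the earlier and shorter of the two data cuts, and its own exposure table does not fit that cut. The protocol sections that plan the analysis carry no such limit, and the SAP does not list one as a change.

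At study end, when the long-term data exist, the visible SAP leaves separate double-blind and open-label tables. For the 106 alirocumab-arm patients the open-label tables restart the clock at Week 12, and they omit anyone who stopped before open-label dosing. Adding the two sets does not give cumulative incidence, because "Multiple occurrences of the same event in the same patient will be counted only once in the tables within a treatment phase": a patient with the same event in both phases would count twice.

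The number of patients with at least 12 months of alirocumab is the stated reason for enrolling 159 rather than the 57 needed for efficacy (Protocol 11.1). No study-end table counts it directly.

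**Working it through.** **The plan's own figures (Protocol 11.1).** A 30% dropout in 12 months under an exponential model gives a hazard of −ln(0.70)/52 = 0.00686 per week. Retention at week w is S(w) = 0.70^(w/52).
- Dropout to Week 64: 1 − 0.70^(64/52) = 35.5% (stated 36%).
- Completers: 159 × 0.645 = 102.5 (stated 100).
- Probability of seeing at least one event at rate 0.03 in 100 patients: 1 − 0.97^100 = 95.2% (stated 95%).

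The sizing reproduces.

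**Longest exposure at the Week 24 cut.** SAP 2.4.3.1 uses (last dose + 14 − first dose)/7, with dates in days. Week 24 is Day 169 ± 3.
- Alirocumab arms, dosed on Day 169: (169 + 14 − 1)/7 = 26.0 weeks. With the +3-day window: (172 + 14 − 1)/7 = 26.4.
- No Week 24 visit, cut 169 days after first dose: (169 + 14)/7 = 26.1 weeks.
- Former placebo patients, first alirocumab on Day 85: (169 + 14 − 85)/7 = 14.0 weeks. At the window extremes: (172 + 14 − 82)/7 = 14.9.
- To reach 36 weeks, a dose is needed 36 × 7 − 14 = 238 days (34 weeks) after the first, well beyond the cut.

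Three of six categories (36 to <48, 48 to <60, 60 or more) are therefore empty for everyone, and four of six for former placebo patients. If the Week 24 dose is not counted, the alirocumab arms reach only (141 + 14 − 1)/7 = 22 weeks nominally, and four of six are empty for everyone.

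With study-end data, last doses at Week 60 or 62 give the alirocumab arms 62 or 64 weeks, and every category can be reached.

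**What the open-label tables leave out, at the protocol's hazard.**
- Alirocumab-arm patients stopping before Week 12: S(12) = 0.921, so 106 × 0.079 = 8.4.
- Double-blind alirocumab time: (1 − 0.921)/0.00686 = 11.52 weeks per patient; 106 × 11.52/52.18 = 23.4 patient-years.
- Open-label time: (0.921 − 0.645)/0.00686 = 40.28 weeks per randomized patient; 159 × 40.28/52.18 = 122.7 patient-years.
- Share outside the open-label tables: 23.4/146.1 = 16%.

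**Whether the open-label exposure table can supply the 12-month count.** Its top category is 48 weeks or more.
- Open-label completers on the +14-day formula: (60 − 12) + 2 = 50 weeks on Q4W, and (62 − 12) + 2 = 52 weeks if up-titrated.
- Expected in the top category, taken as dosed at Week 60: 159 × 0.663 = 105.
- At least 12 months from first alirocumab dose: 106 × 0.700 + 53 × 0.645 = 74 + 34 = 108.
- Alirocumab-arm patients stopping between Weeks 52 and 60: 106 × (0.700 − 0.663) = 4. On Q4W their last dose is at Week 52 or 56. They have 54 or 58 weeks from first dose but score 42 or 46 in the open-label table.

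The top open-label category is thus a near proxy. A 52-week cut on the +14-day formula would be worse. If nobody is up-titrated, former placebo completers score 50 weeks and the count is only 106 × 0.700 = 74. If everybody is, it is 106 × S(50) + 53 × S(62) = 75.2 + 34.6, about 110.

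**The case against.** The strongest counter-argument is that the SAP may be following the protocol. A note in Protocol 9.2, directly above the definition of the combined period, ties the treatment-emergent periods for long-term safety to the first analysis. Protocol 11.5 explains why a 24-week data set matters: it is required for the Japanese application. That note is the only protocol text giving these periods a timing. It stands as a real ambiguity. However, it does not exclude a second run, and neither Protocol 11.4.3 nor 11.5.2 limits the analysis.

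Second, no safety data are lost. Patients who stop before open-label dosing stay in the double-blind tables, by arm and beside concurrent placebo, with follow-up to 70 days after last dose. The 16% describes where time is tabulated. This is correct; what is absent is the cumulative summary.

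Third, the sizing of 159 rests on about 102 patients retained to Week 64, and the open-label category of 48 weeks or more (about 105) tracks that closely. This stands too. The four misplaced patients also assume Q4W: an up-titrated patient last dosed at Week 58 scores 48 weeks and enters the top category.

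Fourth, the drafting is loose. Disposition and baseline summaries of the alirocumab safety population carry no limit. The injection-site and antibody sections mention the exposed period without repeating it. Read literally, the sentence in SAP 2.1.4 also covers the on-study periods used for deaths. Parts of SAP 3 and 4 are redacted and Appendix B was not available. Hidden text could add analyses, but these would conflict with the repeated visible restriction.

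**Conclusion.** The concern holds. The exposure table contradicts its own data cut whatever the dropout: three of six categories cannot be filled, and that is the minimum. On the visible text, study end has no safety table running from first alirocumab dose for the 106 alirocumab-arm patients and no direct count of patients treated for 12 months.

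The figures of 8 early stoppers, 23 of 146 patient-years and 4 misplaced patients assume the protocol's exponential hazard, and the last also assumes Q4W dosing. The consequence is confined to descriptive safety reporting. The primary and key secondary inference, the sample size and the capture of events are untouched. It should be corrected because the long-term safety requirement accounts for the increase from 57 to 159 patients.

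**What to change.** Remove the first-step-only limits in SAP 2.1.4, 2.4.3, 2.4.5 (with its laboratory and vital-sign subsections) and 2.4.6. Run the alirocumab exposed analyses at both steps, with the second as the final long-term safety analysis. Clarify that the on-study periods in 2.1.4 are not restricted.

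Report the number of patients with at least 12 months of alirocumab under a stated rule that matches the sizing. One example is last dose plus the planned dosing interval minus first alirocumab dose, at least 52 weeks, with a stated visit-window allowance. Former placebo completers on schedule then score (60 − 12) + 4 = 52 weeks on Q4W or (62 − 12) + 2 = 52 if up-titrated.

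If the first-step limit is intended, declare it in SAP 1.5 and 1.6 and delete the unreachable categories. Either way, reconcile Protocol 9.2 and 11.4.3 with SAP 2.1.4, 2.4.3.1 and 2.4.5.

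The cost is SAP wording, one counting rule, and a re-run at the final lock of tables already needed for the first step.

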2.1.4.1 Adverse events variables

AEs (including SAEs and AESI) are recorded from the time of signed informed consent until the end of the study. All AEs diagnosed by the Investigator, irrespective of the result of the adjudication for CV events, will be reported and described.

All AEs will be coded to a lower-level term (LLT), preferred term (PT), high-level term (HLT), high-level group term (HLGT), and associated primary system organ class (SOC) using the version of Medical Dictionary for Regulatory Activities (MedDRA) currently in effect at Sanofi at the time of the database lock for the first step analysis.

Adverse event observation period

- Pre-treatment AEs are AEs that developed or worsened or became serious during the pre-treatment period.
- Double-blind TEAEs are AEs that developed or worsened or became serious during the double-blind TEAE period.
- Double-blind post-treatment AEs are AEs that developed or worsened or became serious during the double-blind post-treatment period.
- Open-label TEAEs are AEs developed or worsened or became serious during the open-label TEAE period.
- Open-label post-treatment AEs are AEs that developed or worsened or became serious during the open-label post-treatment period.
- Alirocumab exposed TEAEs are AEs developed or worsened or became serious during the alirocumab exposed TEAE period.

AESI include the following AEs:

AESIs are AEs (serious or non-serious) that need to be monitored, documented, and managed in a pre-specified manner described in the protocol. In this study, AESIs are the following (their complete descriptions are provided in the protocol):

- Local injection site reactions, selected using e-CRF specific tick box on the AE page;
- Allergic events:
 - General allergic events will be tabulated. Events will be selected using standardized MedDRA query (SMQ) "hypersensitivity" (broad and narrow) excluding the following preferred terms linked to local injection site reactions ("infusion site dermatitis", "infusion site hypersensitivity", "infusion site rash", "infusion site urticaria", "injection site dermatitis", "injection site hypersensitivity", "injection site rash", "injection site urticaria" and "injection site vasculitis");
 - General allergic events and local allergic reactions at IMP injection site will be described. This selection will be based on the above selection for general allergic event and on the following selection of PT from the symptoms complementary form for local injection site reaction ("Injection site dermatitis", "Injection site hypersensitivity", "Injection site oedema", "Injection site rash", "Injection site urticaria", "Injection site eczema", "Injection site vasculitis", "Injection site swelling", "Infusion site dermatitis", "Infusion site hypersensitivity", "Infusion site oedema", "Infusion site rash", "Infusion site urticaria", "Infusion site swelling")

- ALT ≥ 3 ULN (if baseline ALT <ULN) or ALT ≥ 2 times the baseline value (if baseline ALT \geq ULN), selected using laboratory data;
- Hemolytic anemia, selected using e-CRF specific tick box on the AE page and confirmed final diagnosis provided in the AE complementary form;
- Neurologic events selected using SMQs “demyelination” (broad and narrow), “peripheral neuropathy” (broad and narrow), and “Guillain-Barre syndrome” (broad and narrow) excluding the following preferred terms “acute respiratory distress syndrome”, “asthenia”, “respiratory arrest” and “respiratory failure”;
- Neurocognitive events, selected using a company MedDRA query (CMQ), based on the following 5 HLGTs: “deliria (including confusion)”, “cognitive and attention disorders and disturbances”, “dementia and amnestic conditions”, “disturbances in thinking and perception”, and “mental impairment disorders”
- Ophthalmologic events selected using SMQs “optic nerve disorders” (broad and narrow), “retinal disorders” (narrow), and “corneal disorders” (narrow);
- Overdose with IMP (symptomatic or asymptomatic). The selection is based on the preferred terms “Accidental overdose” and “Intentional overdose” and the tick box “Overdose with IMP auto-injectors” in the AE complementary e-CRF form;
- Overdose with NIMP (symptomatic or asymptomatic). The selection is based on the preferred terms “Accidental overdose” and “Intentional overdose” and the tick box “Other medications” in the AE complementary e-CRF form
- Pregnancy of female patient/subject (including male subject’s partner) selected using appropriate MedDRA codes.
- [REDACTED]

In addition the following grouping of events will be provided:

- Hepatic disorder events using SMQ “Hepatic disorder”
- Diabetes mellitus or diabetic complications using HLGT “diabetes complications” (including PTs pertaining to the secondary SOC included in the HLGT), HLT “diabetes mellitus”, and HLT “carbohydrate tolerance analyses (incl diabetes)” excluding PTs “blood glucose decreased” and “Glycosylated haemoglobin decreased” and including the PTs “hyperglycaemia”, “Hyperglycaemic unconsciousness” and “Hyperglycaemic seizure” from the HLT “Hyperglycaemic conditions NEC”.
- Cataract using HLT “Cataract conditions”

Cardiovascular events

Suspected CV events that occur from randomization until the follow up visit will be submitted to the Clinical Events Committee (CEC) for adjudication.

Adjudicated CV events include all CV AEs and CV procedures positively adjudicated as defined in the CEC charter. The following categories will be described:

- CHD death
- Non-fatal MI,
- Fatal and non-fatal ischemic stroke,
- Unstable angina requiring hospitalization,
- Congestive heart failure requiring hospitalization,
- Ischemia driven coronary revascularization procedure.

